17.3.2 Safety Endpoints

1. Incidence (severity and causality) of any local and systemic AEs.
2. Number of subjects with presence (and severity) of the following LSRs: burning/stinging, edema, and folliculitis at each time point (except Screening).
3. Changes from Baseline in vital signs at Visit 6/EOT and subsequent visits (if applicable).
4. Changes from Screening in clinical laboratory tests (chemistry, hematology, and urinalysis) at Visit 6/EOT and subsequent visits (if applicable).

17.3.3 Photography

Photography taken at all visits by the sites only shall be used as supportive documentation of efficacy and safety outcomes for this study. An independent photo review may be performed at the discretion of the Sponsor.

17.4 Statistical Methods

All statistical processing will be performed using SAS®. Summary tables (descriptive statistics and/or frequency tables) will be provided for Screening and/or Baseline variables, efficacy variables, and safety variables. Continuous variables will be described by descriptive statistics (n, mean, median, SD, minimum, and maximum). Frequency counts and percentage of subjects within each category will be provided for categorical data. Summaries will be provided for each treatment group.

17.4.1 Efficacy Analyses

The efficacy analyses will be conducted on the ITT and PP populations.

Product Name: DUR-928 Topical Solution
Sponsor Name: Therapeutics, Inc.

Protocol: C928-015
Protocol Date: May 22, 2019, v4.0

For endpoints of change from Baseline, the comparison between DUR-928 and VEH will be conducted using a paired t-test with a significant alpha level of 0.05.

For endpoints of treatment success outcomes, the comparison between DUR-928 and VEH will be conducted using McNemar's test with a significant alpha level of 0.05.

The within subject difference in the change scores and Target Plaque Comparison score between DUR-928 and VEH will also be calculated and summarized descriptively.

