3. OBJECTIVE

The primary objective of this trial is to determine and compare the safety, tolerability, and efficacy of DUR-928 with that of the vehicle control in subjects with plaque psoriasis with occlusion.

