4. STUDY DESIGN

This is a multicenter, randomized, double-blind, vehicle-controlled, paired-plaque, proof of concept comparison study of DUR-928 in subjects with stable mild to moderate plaque psoriasis. Eligible subjects must have two similar contralateral Target Plaques as described in [Section 5.1.1](#). Approximately 20 subjects will be enrolled at approximately three study sites to obtain about 15 evaluable subjects. The maximum proportion of subjects to be enrolled with mild plaque psoriasis is approximately 25% of the total enrolled subjects.

Each subject will receive both of the following treatments with occlusion:

1. DUR-928 Topical Solution,  and
2. Vehicle Topical Solution

Subjects will be instructed to apply the test articles once daily to the two Target Plaques at approximately the same time and follow the instructions for application and occlusion. Subjects will be allowed to use triamcinolone cream, 0.1% and/or over the counter (OTC) hydrocortisone ointment or cream 1% or 0.5% on the face/neck, trunk, buttocks, and lower extremities only no more than twice daily. Subjects will also be allowed to use a bland emollient on all areas (face/neck, trunk, buttocks, lower extremities, upper extremities) that are not designated Target Plaques no more than twice daily. There will be nine study visits. Efficacy will be measured through Investigator's Global Assessment (IGA), Clinical Signs and Symptoms of Psoriasis including Local Psoriasis Severity Index (LPSI), Target Plaque Area, and Target Plaque Comparison assessments by the investigator or designee in a blinded fashion. Efficacy will also be measured using the subject-assessed Numeric Rating Scale (NRS) for Pruritus. Safety will be measured by brief physical examinations, vital signs, clinical laboratory tests, urine pregnancy tests (UPTs, if applicable), local skin reactions (LSRs), and adverse events (AEs).

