17.3 Endpoints

17.3.1 *Efficacy Endpoints*

For each endpoint listed below the change from Baseline will be calculated for each treatment at Visits 3, 4, 5, 6, 7, 8, and 9 and summarized. The within subject difference in the change from Baseline scores between DUR-928 and VEH will also be calculated at each visit and summarized as the proportion of subjects in which DUR-928 is better than VEH, DUR-928 is the same as VEH, and DUR-928 is worse than VEH.

1. IGA Score.
2. Clinical Signs of Psoriasis (plaque elevation, scaling, and erythema).
3. LPSI (as a sum of all three parameters including plaque elevation, scaling, and erythema).
4. Target Plaque Area (will only be calculated at Visits 4, 6, and 9).
5. NRS for Pruritus (will only be calculated at Visits 4, 6, and 9).

Treatment success outcomes will also be calculated and summarized as follows for each treatment at Visits 3, 4, 5, 6, 7, 8, and 9.

1. IGA – proportion of subjects with Target Plaques achieving a score of 0 or 1 representing “clear” or “almost clear” with at least 2-grade decrease in severity relative to Baseline.

2. Clinical Signs of Psoriasis – for each clinical sign (plaque elevation, scaling, erythema) the proportion of subjects with Target Plaques achieving a score of 0 or 1 representing “clear” or “almost clear” with at least 2-grade decrease in severity relative to Baseline.
3. NRS for Pruritus – proportion of subjects with Target Plaques that have a Baseline NRS score ≥ 4 and at least a 4 point decrease in NRS score relative to Baseline (will only be calculated at Visits 4, 6, and 9).
4. Target Plaque Area – proportion of subjects with Target Plaques achieving a 50% reduction in Target Plaque Area from Baseline (will only be calculated at Visits 4, 6, and 9).

Additionally, Target Plaque Comparison score results will be summarized at Visits 2, 3, 4, 5, 6, 7, 8, and 9 as the proportion of subjects with each score including, 1A = Target Plaque A is better than Target Plaque B, 0 = Target Plaque A is the same as Target Plaque B, and 1B = Target Plaque A is worse than Target Plaque B.

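### Thirteen efficacy outcomes are each tested at 0.05 in two populations, and none is named as the one that answers the primary objective

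*Combined protocol and SAP*

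**What the plan says.** Section 3 (Objective) reads: "The primary objective of this trial is to determine and compare the safety, tolerability, and efficacy of DUR-928 with that of the vehicle control". Efficacy against vehicle is therefore inside the primary objective, but no endpoint, visit or population is attached to it.

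Section 17.3.1 lists the outcomes. For the change scores, "the change from Baseline will be calculated for each treatment at Visits 3, 4, 5, 6, 7, 8, and 9 and summarized". With the three signs counted separately there are seven: IGA, plaque elevation, scaling, erythema, LPSI, Target Plaque Area and pruritus NRS. For the responder outcomes, "Treatment success outcomes will also be calculated and summarized as follows for each treatment at Visits 3, 4, 5, 6, 7, 8, and 9". There are six: IGA, the three signs, NRS and area. Area and NRS are restricted to Visits 4, 6 and 9 in both lists.

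Section 17.4.1 sets the analysis. "The efficacy analyses will be conducted on the ITT and PP populations". For change scores, "the comparison between DUR-928 and VEH will be conducted using a paired t-test with a significant alpha level of 0.05"; for success outcomes, "the comparison between DUR-928 and VEH will be conducted using McNemar's test with a significant alpha level of 0.05". A third item is handled differently: "The within subject difference in the change scores and Target Plaque Comparison score between DUR-928 and VEH will also be calculated and summarized descriptively". The synopsis gives the same plan.

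On size, Section 4 says: "Approximately 20 subjects will be enrolled at approximately three study sites to obtain about 15 evaluable subjects". Section 17.1 explains that no sample size was calculated because the study is a pilot. Section 17.2.3 adds that the deviations excluding a subject from PP are settled before unblinding.

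No visible text names a primary efficacy endpoint, visit or population, sets a testing order, or calls the p-values nominal or exploratory. Blacked-out pages cannot be checked.

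**The concern.** A significance level of 0.05 describes one test. The plan attaches it to at least 13 outcomes per population and does not say which result answers the objective. Section 17.4.1 keeps the purely descriptive treatment for the within-subject differences and the Target Plaque Comparison score, so the t-tests and McNemar tests read as tests of significance.

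A proof-of-concept trial informs whether development continues. With about 20 subjects, one isolated p<0.05, for example in a single clinical sign, can easily arise by chance. Without a pre-named analysis, the team could decide after seeing unblinded results which endpoint, visit and population to put forward, and a reader of the report could not tell a planned result from a selected one.

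**Working it through.** **1. The plan's own figure.** One test at 0.05 gives 1 - (1 - 0.05)^1 = 0.05. In the simulation below, LPSI tested alone was significant in 4.9%-5.2% of runs in either direction and in 2.4%-2.7% favouring DUR-928, so the set-up reproduces the stated level. The plan does not state sidedness; two-sided is assumed throughout.

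**2. Count (Section 17.3.1).** At Visit 6/EOT all outcomes are available: 7 change scores + 6 success outcomes = 13 tests per population, and 2 x 13 = 26 over ITT and PP.

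**3. Independence as a reference only.** For seven independent t-tests, either direction: 1 - 0.95^7 = 30.2%. Favouring DUR-928: 1 - 0.975^7 = 16.2%. The endpoints are correlated, so these overstate the rate.

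**4. Seven t-tests with correlation, Visit 6/EOT, one population.** Inputs: n = 15 and 20 (Section 4). Six within-subject differences (IGA, elevation, scaling, erythema, area, NRS) are normal with mean zero and a common correlation r. LPSI is the sum of the three signs (Section 10.1.3). For each score, t = mean / (SD / sqrt(n)), compared with the two-sided 5% critical value on n - 1 degrees of freedom. The documents give no r, so 0.3, 0.5 and 0.8 are assumed. Chance of at least one significant result favouring DUR-928, 40,000 runs per setting (Monte Carlo standard error at most 0.25 points):

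| r | n = 15 | n = 20 |
|---|---|---|
| 0.3 | 12.8% | 12.8% |
| 0.5 | 11.0% | 10.9% |
| 0.8 | 7.4% | 7.2% |

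Against 2.5% for one test, that is 7.2/2.5 = 2.9 to 12.8/2.5 = 5.1 times. In either direction the range is 14.4%-25.2%, against 5%. A separate run of 10,000 per setting agreed within simulation error.

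**5. Adding the six McNemar tests, exact version.** With d discordant subjects all in one direction, the exact two-sided p is 2 x 0.5^d: 0.0625 for d = 5 and 0.03125 for d = 6. At least six are therefore needed. By enumeration, the per-test size at 10%, 20% and 30% discordance is 0.007%, 0.16% and 0.67% for n = 15, and 0.03%, 0.48% and 1.30% for n = 20. Simulated jointly with the t-tests (20,000 runs per setting, assumed success rate 10%-30% per plaque, within-subject correlation 0.5), the totals are 7.3%-13.7% favouring and 14.8%-27.6% in either direction. Exact McNemar tests add little.

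**6. Adding the PP repeat of the seven t-tests.** With 20 subjects in ITT and 15 of them in PP (assumed from Section 4), favouring is 10.2%-17.9%. It is 9.1%-15.9% with 18 in PP and 11.1%-19.4% with 12. The overlap is uncertain, because Sections 5.1.3 and 13.2 replace withdrawn subjects until about 20 complete.

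**The case against.** The strongest reply is that this is openly a small proof-of-concept study with no sample size calculation, no stated success criterion and no claimed overall error rate. Section 17.4.1 sets a per-test level and never offers 0.05 as anything else. The inflated chance matters only if any p<0.05 is read as a signal, and the plan states no such rule. The endpoints also overlap heavily: LPSI is the sum of three of the other scores, and IGA weighs the same three signs.

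Much of this stands. Strict family-wise control is not called for, and the step 4 figures already allow for correlation. But pilot status is used in Section 17.1 to explain the missing sample size calculation, not to qualify the tests in Section 17.4.1. Nor does the absence of a decision rule help: it is exactly what leaves the choice open.

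Three stronger readings are tempting and not supported:

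- A reader might infer that every outcome is tested at every listed visit: 41 t-tests (5 x 7 + 2 x 3) plus 34 McNemar tests (4 x 7 + 2 x 3), or 75 per population, which under independence gives 1 - 0.95^75 = 97.9%. Section 17.3.1 says that outcomes are calculated and summarized at those visits; Section 17.4.1 does not say at which visits they are tested, and the tests are not independent.
- A reader might use asymptotic McNemar tests, which raise the joint favouring figure to 10.0%-20.8%. The plan does not say which version is meant.
- A reader might infer that the PP population itself can be shaped after unblinding. Section 17.2.3 rules that out. What stays open is whether ITT or PP is given weight.

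**Conclusion.** The point holds in a limited form. The plan tests 13 outcomes per population at 0.05 and leaves undecided which endpoint, visit and population answers the efficacy part of the primary objective. On the narrow reading of Visit 6/EOT in one population, the seven t-tests alone carry about a 7%-13% chance under no effect of a significant result favouring DUR-928, roughly three to five times that of one test, and about 14%-25% in either direction.

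This rests on assumed between-endpoint correlations of 0.3-0.8, two-sided tests, normal data and 15-20 subjects. The rate is higher once the PP repeat is counted, and would be higher again if other visits are tested; no figure for all visits can be relied on. This limits how an efficacy result can be interpreted. It is not an arithmetic error or a contradiction in the plan, and it does not invalidate the trial.

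**What to change.** Before unblinding, name one primary efficacy analysis in Sections 17.3.1 and 17.4.1 and in the synopsis: one endpoint, one visit, one population, two-sided 0.05. The choice is the sponsor's; LPSI change from Baseline at Visit 6/EOT in ITT is one example. Report all other endpoints, visits and the PP repeat as supportive, with estimates, 95% confidence intervals and nominal p-values. The named analysis then has its stated 5% error rate (2.5% favouring DUR-928), and no adjustment of the other tests is needed.

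Merely labelling every p-value nominal would be honest but weaker, since it still would not say which result answers the objective. The visits tested, the sidedness of the supportive tests and the McNemar version are separate specification gaps that the same edit could close.

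The cost is about one paragraph of wording, with no extra data, visits or subjects. The downside is that the other endpoints can no longer be called significant on their own.

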17.4.1.1 Dosing Compliance

Descriptive statistics will be used to summarize for each treatment group the duration of treatment (defined as last dose date – first dose date +1), the total number of applications (determined from the doses reported in the Subject Diary), and the percent of expected doses applied for the ITT and PP populations. Subjects who apply at least **CCI** of the expected total number of applications and have no other evidence of material dosing non-compliance will be considered to be compliant with test article dosing.

17.4.2 *Safety Analyses*

All safety analyses will be performed on the Safety population.

Safety endpoints will be summarized by descriptive statistics including sample size, mean, SD, median, minimum, and maximum; or by frequency and percentage as appropriate.

Extent of Exposure

Descriptive statistics will be used to summarize the extent of exposure. The total amount of test article used by each subject (prescribed amount of test article multiplied by the number of doses applied) and the mean daily amount of test article applied (total amount of test article applied divided by the duration of treatment) will be calculated.

Physical Examinations

Findings from physical examinations (head and neck, cardiovascular, dermatological, respiratory, gastrointestinal (abdomen), and gross motor and gait) will be recorded in medical history (from assessment at Visit 1/Screening) or as AEs (from assessment at Visit 6/EOT [and subsequent visits, if applicable]).

Vital Signs

Descriptive statistics of vital signs (temperature, systolic and diastolic blood pressure, heart rate, and respiration rate) at Visit 1/Screening, Visit 2/Baseline, Visit 6/EOT (and subsequent visits, if applicable) will be provided by treatment group.

Clinical Laboratory Tests

Clinical laboratory tests will be evaluated for any material changes during the study period. All laboratory data (hematology, chemistry, and urinalysis) will be listed and reported in

Product Name: DUR-928 Topical Solution
Sponsor Name: Therapeutics, Inc.

Protocol: C928-015
Protocol Date: May 22, 2019, v4.0

the units received by the laboratory. Shift tables by analyte and by out of range flag will be presented to facilitate the evaluation of change from Visit 1/Screening to Visit 6/EOT (and subsequent visits, if applicable).

Local Skin Reactions

LSRs (burning/stinging, edema, and folliculitis) will be summarized by frequency of each individual LSR for each treatment group.

Adverse Events

All AEs reported during the study will be listed, documenting course, severity, investigator assessment of the relationship to the test articles, and outcome. Verbatim terms on the eCRFs will be linked to PTs and SOC using the MedDRA mapping system. The PTs and SOC will then be tabulated. All reported AEs will be summarized by the number of subjects reporting AEs, SOC, PT, severity, and relationship to test article by treatment group.

Urine Pregnancy Tests

Results from UPTs (if applicable) at Visit 1/Screening, Visit 2/Baseline, and Visit 6/EOT will be provided in a listing.

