10.2 Safety Evaluations

10.2.1 *Brief Physical Examination*

A brief physical exam will be performed at Visit 1/Screening and Visit 6/EOT. The exam will include examination of head and neck, dermatological, cardiovascular, respiratory, gastrointestinal (abdomen), and gross motor and gait. Abnormalities at Visit 1/Screening will be recorded as medical history. Any new or worsening abnormalities at Visit 6/EOT (and subsequent visits, if applicable) will be recorded as AEs. Directed physical exams will be performed at subsequent follow-up visits until the finding has resolved or stabilized in the opinion of the investigator.

10.2.2 *Vital Signs*

Vital signs including temperature, systolic and diastolic blood pressure, heart rate, and respiration rate will be measured at Visit 1/Screening, Visit 2/Baseline, and Visit 6/EOT. Assessments will also be performed at any subsequent follow-up visits if the results from the preceding visit are materially abnormal and clinically significant in the opinion of the investigator. Assessments will be made after the subject has rested in a seated position for at least five minutes. Height and weight will only be measured at Visit 1/Screening.

10.2.3 *Local Skin Reactions*

LSRs (burning/stinging, edema, and folliculitis) will be assessed for each Target Plaque at every visit (except Screening) using a 4-point ordinal scale (0=none, 1=mild, 2=moderate, 3=severe). Only LSRs that require medical intervention (e.g., prescription medication) will be documented as AEs. Any LSRs that are not listed above will be recorded as AEs.

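### Local skin reactions are planned as separate frequencies per treatment; a paired table would add the precision, within-subject pattern and change from pre-dose that those frequencies leave out

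*Combined protocol and SAP*

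**What the plan says.** Section 3 sets the objective: to "determine and compare the safety, tolerability, and efficacy of DUR-928 with that of the vehicle control". Section 4 describes a paired-plaque design in which "Each subject will receive both of the following treatments with occlusion".

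The LSR data are paired too. Section 10.2.3 states that "LSRs (burning/stinging, edema, and folliculitis) will be assessed for each Target Plaque at every visit (except Screening) using a 4-point ordinal scale". Section 9.3 adds that at Visit 2 they are graded before the first application and again 15 minutes after it.

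The reporting does not use the pairing. The endpoint in section 17.3.2 is "Number of subjects with presence (and severity) of the following LSRs", counted at each time point after Screening. The analysis in section 17.4.2 is that "LSRs (burning/stinging, edema, and folliculitis) will be summarized by frequency of each individual LSR for each treatment group", and the synopsis says the same. Safety endpoints in general are to be summarized descriptively.

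For efficacy the plan does use the pairing. Section 17.3.1 says: "The within subject difference in the change from Baseline scores between DUR-928 and VEH will also be calculated at each visit", reported as the share of subjects in whom DUR-928 did better than, the same as or worse than vehicle. Section 17.4.1 adds a paired t-test for changes and McNemar's test for treatment success. None of these is extended to LSRs in the readable text.

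**The concern.** LSRs carry much of the tolerability evidence. Under section 10.2.3 the three graded reactions become adverse events only if they need medical intervention, so milder ones appear only in the LSR tables.

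Both plaques are occluded and both receive the same excipients. A subject who reacts on both plaques suggests vehicle, occlusion or individual susceptibility. A subject who reacts only on the DUR-928 plaque suggests the drug. Totals per treatment do not separate these two patterns.

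The pre-dose grade is also left unused at subject level. Section 17.3.2 defines changes for vital signs and laboratory tests, which this design cannot attribute to one treatment. It defines none for LSRs, which it can attribute. A reaction present before dosing and still present later is counted again at each visit, and the counts do not show which subjects got worse.

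A reader could not rebuild the pairs from the specified outputs. Section 17.4.2 names listings for adverse events, laboratory data and pregnancy tests, but not for LSRs.

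**Working it through.** The plan states no LSR rate, power or sample-size calculation, so there is no figure to reproduce. The question is what the planned counts determine. The numbers of pairs (about 15 evaluable, about 20 enrolled) come from section 4. All reaction counts below are assumptions.

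**Notation.** Of n subjects, a react on both plaques, b on the DUR-928 plaque only and c on the vehicle plaque only. The planned table shows a + b and a + c.

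**Difference.** (a + b)/n − (a + c)/n = (b − c)/n. The unknown a cancels, so the planned table fixes the size and direction of the difference.

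**Precision.** The large-sample (Wald) standard error is √[(b + c) − (b − c)²/n]/n. The exact two-sided sign-test p is 2·P(X ≥ max(b, c)) with X ~ Binomial(b + c, ½). Both depend on b + c, which the planned table does not show.

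**Illustration, n = 15, 7 v 2 reactions.** The difference is (7 − 2)/15 = 33% in every row.

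| a | b-c split | Exact p | Wald SE | Wald 95% CI |
|---|---|---|---|---|
| 2 | 5-0 | 2 × 1/32 = 0.0625 | √(5 − 25/15)/15 = 0.122 | 9% to 57% |
| 1 | 6-1 | 2 × 8/128 = 0.125 | √(7 − 25/15)/15 = 0.154 | 3% to 64% |
| 0 | 7-2 | 2 × 46/512 = 0.180 | √(9 − 25/15)/15 = 0.181 | −2% to 69% |

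The Wald intervals for 5-0 and 6-1 exclude zero although the matching exact tests do not reject at 0.05. A large-sample interval is therefore unsuitable at this size.

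**Other assumed margins.**

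| n | Reactions, DUR-928 v vehicle | Difference | Possible splits (exact p) |
|---|---|---|---|
| 15 | 7 v 1 | 40% | 7-1 (0.070), 6-0 (0.031) |
| 20 | 8 v 2 | 30% | 8-2 (0.109), 7-1 (0.070), 6-0 (0.031) |
| 20 | 6 v 2 | 20% | 6-2 (0.289), 5-1 (0.219), 4-0 (0.125) |

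If no vehicle plaque reacts, then a = c = 0 and the margins determine the pairs completely. With one vehicle reaction only two tables are possible. For a single yes/no reaction, the loss therefore needs at least one reaction on each treatment.

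**Power of a formal test.** At least six discordant pairs, all in one direction, are needed for p < 0.05 (2 × (½)⁶ = 0.031; five give 0.0625). With assumed discordant probabilities of 0.30 v 0.05, exact power is 17% at n = 15 and 32% at n = 20. With 0.50 v 0.05 it is 60% and 79%.

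**The case against.** The strongest reply is that the planned table already compares the treatments. Both have the same subjects as denominator, and the difference in frequencies is the paired difference. That stands. A reader might infer that the tolerability objective cannot be answered from these counts, or that one table could come from pairs that point to DUR-928 or from pairs that do not. The documents do not support either reading: (b − c)/n is fixed by the planned counts.

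Three further replies have weight.

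- Descriptive safety reporting is usual in a pilot of this size, section 17.1 makes no formal sample-size claim, and a test would have low power. This stands as a reason not to require a test. It is no reason to omit a cross-tabulation, which is itself descriptive.
- Pre-dose reactions are not hidden, because section 17.3.2 reports each time point after Screening and the pre-dose count can sit beside later ones. This stands for totals, but does not show which subjects rose.
- LSRs are not the only safety measure with a contralateral control. A local adverse event at one plaque has one too, and section 17.4.2 summarizes adverse events by treatment. This also stands.

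Finally, the plaque-level grades are collected whatever the plan says, so the table could be produced at reporting. But the summary grade and the time window would then be chosen after the data are seen.

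**Conclusion.** The point holds as an omission from the analysis plan. The planned LSR frequencies give the size and direction of the treatment difference. They do not give its precision, do not separate reactions on both plaques from reactions on the DUR-928 plaque only, and do not identify subjects who rose above their pre-dose grade.

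The size depends on assumed counts. In the examples the same margins are compatible with exact p from 0.06 to 0.18 (7 v 2 of 15) or 0.03 to 0.11 (8 v 2 of 20), with the difference unchanged. In the first of these no split reaches 0.05, so the exact test's conclusion at that level would not change. If vehicle plaques rarely react, little is lost on precision and pattern.

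No stated figure is wrong, and no efficacy result or analysis population is affected. This is a cheap improvement worth making.

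**What to change.** Add one descriptive paired table to section 17.4.2, fixed before unblinding:

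- For each LSR and each plaque, take the worst post-dose grade on treatment, from the Visit 2 post-dose assessment through Visit 6, and its rise over the pre-dose Visit 2 grade.
- Class each subject as DUR-928 worse, same or vehicle worse, in the format that section 17.3.1 already uses for efficacy. Split the same category into no rise on either plaque and equal rise on both, so that shared reactions are visible.
- Report the counts and the paired difference in proportions (DUR-928 worse minus vehicle worse) with an exact or score 95% interval, not Wald. An exact sign test is optional.
- Keep the by-visit frequencies, including Visits 7 to 9, as supporting tables.

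The cost is one extra table from data already collected. Its intervals will be wide at about 15 to 20 subjects.
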